The preceding table summarizes the planned dose levels. The primary objective of the dose escalation component of the study is to define the maximum tolerated dose (MTD) of the triple combination of dabrafenib, trametinib, and AT13387. Dose escalation will follow a standard 3+3 design beginning in dose level 1. The doses of dabrafenib and trametinib for Dose Level 1 were selected based upon the results of the phase I study showing excellent tolerability and safety, and that this combination appears to be associated with a reduced incidence and severity of *some* of the toxic effects of monotherapy with either a BRAF or MEK inhibitor., as well as excellent clinical activity. (Flaherty *et al.* 2012) Of note, the first dose cohort (dose level 1) incorporates a trametinib dose of 1 mg daily as opposed to the FDA-approved dose of 2 mg daily. This dose was chosen due to the theoretical overlapping ocular toxicity of trametinib and AT13387.

It is conceivable that additional cohorts may be necessary to pick an optimal treatment regimen with the three agents. As such, if toxicity is seen at a dose level where dose modification is necessary and the prior, lower dose level was treated without DLT, then additional dose cohorts between the two dose levels will be considered (see section 5 for details of this process). If the toxicity is determined to be related to dabrafenib (i.e. palmar-plantar erythrodysesthesia syndrome, arthralgia) then the dose of dabrafenib will be reduced first to 75 mg BID and then increased to 100 mg BID if that first dose level is tolerated. If the toxicity is determined to be related to trametinib, then the dose of trametinib will be reduced to 1 mg QD (if a dose higher than 1 mg QD is being evaluated in the dose cohort) and then increased to 1.5 mg QD if that first dose level is tolerated. If the toxicity is determined to be related to AT13387 then the dose will be reduced by 1 dose cohort. At the end of the planned enrollment to the phase 1 portion of the study, a complete review of the PK data and safety will occur before cohort expansion at the MTD.

TABLE OF CONTENTS

SCHEMA.....	3
1. OBJECTIVES	6
1.1 Phase I Objectives.....	6
2. BACKGROUND	6
2.1 BRAF mutant melanoma	6
2.2 CTEP Agents	7
2.3 Rationale	37
2.4 Correlative Studies Background	39
3. PATIENT SELECTION	40
3.1 Eligibility Criteria	40
3.2 Exclusion Criteria	42
3.3 Inclusion of Women and Minorities	45
4. REGISTRATION PROCEDURES	46

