5.2 Definition of Dose Limiting Toxicity

Dose-limiting toxicity (DLT) is based on the CTEP Active Version 5 of the NCI Common Terminology Criteria for Adverse Events (CTCAE). DLT refers to toxicities experienced during the first cycle of treatment between days 1-28. A DLT must be considered to be at least possibly related to study drug(s) will be defined as follows:

- Any grade 4 toxicity
- Grade 3 (or grade 2 intolerable) non-hematologic toxicity
- Grade ≥ 3 neutropenia with fever $> 38.5^{\circ}\text{C}$
- Grade 3 thrombocytopenia with clinically significant bleeding
- Furthermore, grade 2 intolerable/grade 3 fatigue that results in hospitalization should be considered a DLT.
- Intolerable AEs are toxicities deemed to lead to a missing dose of AT13387 or more than 25% of dabrafenib/trametinib in the first cycle.

In general, all Grade 3 or intolerable grade 2, non-hematological toxicities regardless of duration are considered DLT. However, the following Grade 3 toxicities will not be considered a DLT.

- The appearance of cutaneous squamous cell carcinoma or keratoacanthoma will not be considered a dose limiting toxicity as these are commonly observed with dabrafenib.
- Grade 3 fatigue persistent for ≤ 7 days
- Grade 3 nausea, vomiting, or diarrhea persisting ≤ 72 hours with maximum supportive care
- Grade 3 electrolyte events if they are resolved with replacement within 24 hours
- Lymphopenia regardless of grade
- The following grade 3 laboratory abnormalities will not be considered dose limiting if they return to baseline within 7 days: elevated bilirubin, AST, ALT, cholesterol, amylase, lipase, creatinine and hypertriglyceridemia

Management and dose modifications associated with the above adverse events are outlined in Section 6.

Dose escalation will proceed within each cohort according to the following scheme. Dose-limiting toxicity (DLT) is defined above.

Table 5.2. Dose escalation table

Number of Patients with DLT at a Given Dose Level	Dose Escalation Rule
0 out of 3	Proceed to the next dose level and enroll 3 patients
1 out of 3	Enroll and treat 3 additional patients at this dose level.
≥ 2 out of 3	Dose escalation will be stopped. The MTD will be one dose below this dose level. Three (3) additional patients will be entered at the next lower dose level if only 3 patients were treated previously at that dose.
1 out of 6	Proceed to the next dose level.

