13. STATISTICAL CONSIDERATIONS

13.1 Study Design/Endpoints

This is a phase I trial of the combination of dabrafenib, trametinib, and AT13387 in patients with BRAF-mutant advanced solid tumors. The primary objective of the study is to determine the maximum tolerated dose (MTD) of the combination; secondary objectives will provide preliminary estimates of efficacy and toxicity. The escalation and stopping rules imply that the incidence rate for DLT will be less than 33% at the MTD. Following the identification of the MTD, an additional 14 patients will be enrolled in a dose expansion cohort at the MTD.

Toxicities and lab values will be graded according to the NCI Common Toxicity Criteria for Adverse Events (v4.0). Dose-limiting toxicities will be scored and will be defined as in Section 5.2.

Dose escalation will use a standard “3+3” approach, beginning in dose level 1, with dosing and rules for escalation and de-escalation described in the tables below. Tolerability assessments will be based on cycle 1 alone. The MTD is defined as the highest dose level at which 0 or 1 of six patients has experienced a DLT. If an excessive number of toxicities occur at the initial dose level 1, the dose will be reduced to the fall-back dose of -1. If dose level -1 has excessive toxicity, the study will stop.

Dose Level	Dabrafenib [BID/PO]	Trametinib [QD/PO]	AT13387 [D1,8,15/IV]
-1	75 mg	1 mg	180 mg/m ²
1	150 mg	1 mg	180 mg/m ²
2	150 mg	2 mg	180 mg/m ²
3	150 mg	2 mg	220 mg/m ²
4	150 mg	2 mg	260 mg/m ²

Number of Patients with DLT at a Given Dose Level	Dose Escalation Rule
0 out of 3	Proceed to the next dose level and enroll 3 patients
1 out of 3	Enroll and treat 3 additional patients at this dose level
	Dose escalation will be stopped. The MTD will be one dose below this dose

≥ 2 out of 3	level. Three (3) additional patients will be entered at the next lower dose level if only 3 patients were treated previously at that dose.
1 out of 6	Proceed to the next dose level.
≥ 2 out of 6	se escalation will be stopped. The MTD will be one dose below this dose level. Three (3) additional patients will be entered at the next lower dose level if only 3 patients were treated previously at that dose.

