If $\geq 2/3$ or $\geq 2/6$ patients at dose level 1 experience dose limiting toxicities, dose level -1 will be enrolled. If dose level -1 proves too toxic, the study will stop.	Dose escalation will be stopped. The MTD will be one dose below this dose level. Three (3) additional patients will be entered at the next lower dose level if only 3 patients were treated previously at that dose.

The following table shows the probability of escalating the dose for various true, but unknown, rates of unacceptable toxicity.

True DLT Rate	Probability of Dose Escalation
0.10	0.91
0.20	0.71
0.30	0.49
0.40	0.31
0.50	0.17
0.60	0.08

A patient will be replaced if determination of DLT cannot be adequately assessed because of rapid disease progression or if treatment is stopped during the first cycle of therapy for reasons other than toxicity.

When the MTD had been determined, a total of 14 patients will be enrolled in an expansion cohort of patients with BRAF-mutant advanced solid tumors to obtain preliminary toxicity and efficacy estimates. Patients treated at the MTD during the dose escalation phase may be included in the expansion cohort. Toxicity and efficacy rates will be summarized with 90% exact binomial confidence intervals. For a sample of size 14, the confidence intervals will be no wider than 0.48.

The table below summarizes the probabilities of observing at least one patient with a severe or unexpected toxicity in the expansion cohort for a range of incidence rates.

True Incidence of Unexpected or Severe Toxicity	Probability of Observing One or More Patients with Toxicity among 14
0.01	0.13
0.03	0.35
0.05	0.51
0.08	0.69
0.09	0.73
0.10	0.77
0.15	0.90

Secondary endpoints that will be assessed for the 14 patients treated at the MTD are: objective response rate, progression-free survival (PFS), 6-month PFS, and 1-year overall survival (OS).

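### No pre-specified DLT criterion governs the expansion cohort, and the MTD is defined on six patients only, so expansion DLTs trigger no stated action and do not formally change the declared MTD

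*Combined protocol and SAP*

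**What the plan says.** **MTD.** Section 13.1: "The MTD is defined as the highest dose level at which 0 or 1 of six patients has experienced a DLT". It adds: "The escalation and stopping rules imply that the incidence rate for DLT will be less than 33% at the MTD". The rows of Table 5.2, repeated in 13.1, cover three or six patients at a level and go no further.

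**DLT window.** Section 5.2: "DLT refers to toxicities experienced during the first cycle of treatment between days 1-28".

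**Expansion size.** Section 13.1 first says: "Following the identification of the MTD, an additional 14 patients will be enrolled in a dose expansion cohort at the MTD". Later in the same section the 14 are a total, and: "Patients treated at the MTD during the dose escalation phase may be included in the expansion cohort".

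**Use of expansion toxicity.** It is descriptive: "Toxicity and efficacy rates will be summarized with 90% exact binomial confidence intervals". There is also a detection table: "The table below summarizes the probabilities of observing at least one patient with a severe or unexpected toxicity in the expansion cohort".

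**Review tied to the expansion.** The schema text before the table of contents places it ahead of opening: "a complete review of the PK data and safety will occur before cohort expansion at the MTD".

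**General oversight.** Appendix B makes the Protocol Chair responsible for timely adverse-event review. Section 7.3.3 sets expedited reporting of serious events. Section 12.1.1 has data submitted at least every two weeks. None of these carries a DLT threshold or a consequence for accrual or for the MTD.

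**The concern.** The expansion supplies most of the DLT information at the chosen dose: 8 of 14 patients if the 14 are a total, 14 of 20 if they are additional. Yet the plan's rules end before any of these patients is treated. A second DLT in patient 6 stops escalation and moves the MTD down a level; the same event in patient 7 has no stated effect.

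A plan followed to the letter could therefore report 6 of 14 patients with DLT (43%) at a level still labelled the MTD, in a document that says the DLT rate at the MTD is below 33%. Two things are at stake: the safety of patients enrolled after a false clearance, and the MTD statement, which is part of the primary objective. Section 9.1.1 itself says that little is known about interactions within the triple combination.

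**Working it through.** **1. The plan's own figures.** With true DLT rate p, the chance of escalating past a level is (1−p)³ + 3p(1−p)⁵. This gives 0.906, 0.709, 0.494, 0.309, 0.172 and 0.082 at p = 0.10 to 0.60, matching the 13.1 table. The chance of at least one event in 14, 1 − (1−p)¹⁴, also matches that table (for example 0.771 at p = 0.10). The widest 90% exact interval at n = 14 is 0.473, consistent with the stated 0.48.

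**2. Chance that six patients clear a dose.** P(0 or 1 of 6) = (1−p)⁶ + 6p(1−p)⁵.

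| True rate | (1−p)⁶ | 6p(1−p)⁵ | Sum |
|---|---|---|---|
| 0.33 | 0.090 | 0.267 | 0.358 |
| 0.40 | 0.047 | 0.187 | 0.233 |
| 0.50 | 0.016 | 0.094 | 0.109 |

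The 90% exact upper limit is 39% after 0/6 and 58% after 1/6, so clearing six does not establish a rate below 33%.

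**3. Patients treated after the last rule.** Reading the 14 as additional, there are 14 new patients and 6 + 14 = 20 at the level. Reading it as a total with all six counted, there are 14 − 6 = 8 new patients. The rest of the document does not settle it: 4×6 + 14 = 38 matches the accrual table in Section 3.3, while 4×6 + 8 = 32 matches the maximum in Section 13.2.

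At a true rate of 40%, expected further DLTs are 8×0.40 = 3.2 or 14×0.40 = 5.6. P(at least 3 of 8) = 0.68 and P(at least 5 of 14) = 0.72. The plan attaches no action to either result.

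**4. A one-third pause rule.** Boundary on cumulative DLTs at the level: 3 in up to 9, 4 in 10–12, 5 in 13–15, 6 in 16–18, 7 in 19–20. Start from the distribution of DLTs in the first six given 0 or 1, add one patient at a time, and sum the probability of first reaching the boundary.

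| True rate | Pause, 14 in total | Pause, 20 in total |
|---|---|---|
| 0.20 | 0.103 | 0.129 |
| 0.33 | 0.337 | 0.452 |
| 0.40 | 0.493 | 0.648 |
| 0.50 | 0.705 | 0.860 |

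If the first six had exactly one DLT, the 20% row becomes 0.156 and 0.189.

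**5. Patients spared at 40%, 14 in total.** The boundary is first reached at patient 8, 9, 11, 12 or 14 with probability 0.128, 0.166, 0.065, 0.094 and 0.040 (sum 0.493). If outcomes are known at once, the expected number not enrolled is 6×0.128 + 5×0.166 + 3×0.065 + 2×0.094 = about 2.0 of 8. With two patients always pending it is 4×0.128 + 3×0.166 + 1×0.065 = about 1.1. Section 13.2 assumes 2–3 patients per month against a 28-day window, so two or three pending is realistic.

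**The case against.** **Oversight continues.** A reader might infer that expansion DLTs cannot pause accrual or alter the MTD, or that safety is reviewed only before the expansion opens. The documents support neither. Nothing forbids a discretionary pause. The Protocol Chair reviews adverse events, serious Grade 3–5 events carry a 24-hour notice (subject to the listed exceptions), and data arrive every two weeks. Section 5.1 also allows intermediate levels by consensus and amendment when toxicity is seen, and does not expressly confine this to escalation. All of this stands. What is missing is a criterion.

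**Toxicity is reported anyway.** The primary objective covers toxicity and safety profile as well as the MTD, and expansion rates get 90% intervals. A high DLT rate would be visible in the results. It would not formally change the MTD label.

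**DLT scoring is already planned.** The scoring sentence in 13.1 is not limited to escalation patients. This stands, and it makes the fix cheaper.

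**The 31% in the plan's table.** A reader might take this as the chance of a false MTD at a true rate of 40%. It is the chance of escalating past a level. The chance of clearing six is 23%, and that is conditional on reaching the level.

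**The benefit is modest.** The rule misses a 40% dose about half the time with 14 in total, and pending outcomes reduce the number spared. Also, 6 of 14 is about the expected result at 40% only if all 14 are new patients. On the total reading it has a probability of about 15% for 6 or more, given that the six passed. These limits are real; they bear on the size of the gain, not on whether the gap exists.

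**Conclusion.** The point holds in this form: the expansion has no pre-specified DLT criterion, and the declared MTD rests formally on six patients. A level with a true DLT rate of 33%, 40% or 50%, once reached, clears six patients with probability 36%, 23% or 11%, and 8 to 14 more patients are then treated with no trigger. Under the plan as written, the pre-specified chance of a pause is zero at every true rate; discretion remains.

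The calculations assume independent patients with a constant DLT rate. The pause probabilities also assume that the first six passed and that each 28-day outcome is known before the next patient enrols. The one-third benchmark is the plan's own; the exact boundary is a choice. This should be changed, as an inexpensive improvement, and the gap is present under either reading of the expansion size.

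**What to change.** Add one paragraph to Section 13.1:

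- Accrual pauses for review by the sponsor and study chair if cumulative DLTs at the level (Section 5.2 definition, escalation patients at that level included) reach 3 in up to 9, 4 in 10–12, 5 in 13–15, 6 in 16–18, or 7 in 19–20 evaluable patients.
- The final statement of the MTD or recommended dose uses all DLT-evaluable patients at the level.
- State whether the 14 are additional or a total, and bring Sections 3.3, 13.1 and 13.2 into line.
- State how patients with pending 28-day outcomes are handled when the boundary is checked.

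The trigger is a pause for review. It does not terminate the study, and it changes no dose and no individual patient's management.

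**Cost.** No new data, since cycle 1 toxicity is already collected. The chance of an unnecessary pause at a true rate of 20% is 10% (14 in total) to 13% (20 in total), or 16% to 19% if the first six had one DLT. Fewer patients are spared when outcomes are pending at 2–3 enrolments per month.

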13.2 Sample Size/Accrual Rate

The total enrollment of this trial will be between 4 and 32 evaluable patients. The minimum would occur if the triple combination proved too toxic at dose levels 1 and -1 and the trial was stopped during the dose escalation phase. A maximum enrollment of 32 patients reflects four complete dose escalation cohorts of 6 patients each and the expansion cohort of 14 total patients at the MTD. Assuming an accrual rate of 2-3 patients per month, we estimate a maximum enrollment period of 20 months.

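### If the six escalation patients who qualified the MTD are counted in the 14, the cycle 1 DLT rate at the MTD is biased low and its ordinary exact interval has too low an upper limit; Section 13 does not settle whether they are counted

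*Combined protocol and SAP*

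**What the plan says.** All of this is in the combined protocol and SAP.

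- Selection rule (Section 13.1): "The MTD is defined as the highest dose level at which 0 or 1 of six patients has experienced a DLT".
- Expansion (Section 13.1): "a total of 14 patients will be enrolled in an expansion cohort of patients with BRAF-mutant advanced solid tumors", for preliminary estimates of toxicity and efficacy. On overlap: "Patients treated at the MTD during the dose escalation phase may be included in the expansion cohort".
- Interval (Section 13.1): "Toxicity and efficacy rates will be summarized with 90% exact binomial confidence intervals", with a stated maximum width of 0.48 at 14 patients.
- Sample size (Section 13.2): "A maximum enrollment of 32 patients reflects four complete dose escalation cohorts of 6 patients each and the expansion cohort of 14 total patients".
- Against overlap: earlier in Section 13.1, "an additional 14 patients will be enrolled in a dose expansion cohort at the MTD". The accrual table in Section 3.3 totals 38.
- DLT rate the design expects (Section 13.1): "The escalation and stopping rules imply that the incidence rate for DLT will be less than 33% at the MTD".

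Nowhere does the plan adjust for the selection of the six or ask for a separate DLT estimate in newly enrolled patients.

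**The concern.** A level with two or more DLTs in six cannot be the MTD. Patients carried from escalation into the expansion cohort therefore have a DLT count that can only be 0 or 1, whatever the true rate. An exact binomial interval on 14 assumes that each patient's outcome is free to vary. For DLTs that holds for the new patients and fails for the six.

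The error favours the regimen. The DLT rate reported at the dose taken forward would be too low on average, and so would its upper limit. Toxicity at the MTD is part of the primary objective in Section 1.1.1 and one of the two things the expansion is meant to estimate. The point concerns patients who started at the MTD, so it is separate from any effect of intrapatient escalation.

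**Working it through.** **Inputs.** From Section 13.1: the MTD rule (at most 1 DLT in 6), 14 patients analysed, a 90% exact binomial interval (taken as Clopper-Pearson, at most 5% in each tail). From Section 13.2: the maximum of 32. The true DLT rate p at the MTD is not given. It is varied, mainly up to the 33% in Section 13.1.

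**Plan's own figures.** The widest 90% Clopper-Pearson interval at n = 14 is 0.473, which agrees with the stated 0.48. Maximum enrolment is 4 × 6 + 14 − 6 = 32 with six shared patients and 4 × 6 + 14 = 38 without. So 32 implies 6 escalation patients plus 14 − 6 = 8 new ones.

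**Distribution of the six.** Write q = 1 − p. The routes to six patients with at most one DLT are:
- 0/3 then 0/3: q^6
- 0/3 then 1/3: 3pq^5
- 1/3 then 0/3: 3pq^5

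The total is q^6 + 6pq^5 = q^5(1 + 5p), which is P(Bin(6,p) ≤ 1). Given selection, P(0 DLT) = q/(1 + 5p) and P(1 DLT) = 6p/(1 + 5p), so the expected count is 6p/(1 + 5p) instead of 6p.

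**Pooled estimate.** Expected proportion = [6p/(1 + 5p) + 8p]/14.
- p = 0.20: (0.600 + 1.60)/14 = 0.157
- p = 0.30: (0.720 + 2.40)/14 = 0.223
- p = 0.33: (0.747 + 2.64)/14 = 0.242

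**Upper limit.** At n = 14 the planned upper limits are 0.193 for 0 events, 0.297 for 1, 0.385 for 2 and 0.466 for 3. At p = 0.30 the limit misses when the pooled count is 0 or 1:
- P(0) = (0.7/2.5) × 0.7^8 = 0.016
- P(1) = (0.7/2.5) × 8 × 0.3 × 0.7^7 + 0.72 × 0.7^8 = 0.097
- Sum 0.113. For 14 unselected patients it is 0.047.

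| True rate | Expected pooled rate | Upper limit below truth, pooled | Same, 14 unselected | Two-sided coverage, pooled |
|---|---|---|---|---|
| 0.10 | 0.086 | 0% | 0% | 98.2% |
| 0.20 | 0.157 | 6.7% | 4.4% | 92.6% |
| 0.25 | 0.190 | 3.3% | 1.8% | 96.4% |
| 0.30 | 0.223 | 11.3% | 4.7% | 88.6% |
| 0.33 | 0.242 | 8.1% | 2.9% | 91.9% |

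The mean upper limit falls from 0.443 to 0.396 at p = 0.20 and from 0.547 to 0.469 at p = 0.30.

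**One observed result.** For 3 DLTs in 14 the planned interval is 0.06 to 0.47. Inverting the conditional distribution (six truncated at 1, plus Bin(8,p)) gives 0.07 to 0.62.

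**Cross-check.** A full 3+3 was simulated 60,000 times with assumed DLT rates of 0.10, 0.20, 0.30, 0.40 and 0.50 for levels −1 to 4. The mean true rate at the selected MTD was 0.213 and the mean pooled estimate 0.164. The upper limit missed in 6.5% of trials, against 3.0% with 14 new patients.

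**The case against.** **The interval often still covers.** A reader might infer that the planned upper limit misses too often at any rate. The documents and the arithmetic do not support that. For true rates up to 0.333 the upper-tail miss exceeds 5% on only about 20% of the range (0.193 to 0.221, and from 0.297). Two-sided coverage drops below 90% only between about 0.297 and 0.312, with a minimum of 88.2%. The interval moves in steps: the miss is 1.7% at 0.295 and 11.3% at 0.30. Figures such as 85.2% coverage at a true rate of 0.40 lie above the rate that Section 13.1 associates with the MTD. All of this stands. What remains is the downward bias at every rate above 0 and an upper limit that is lower on average.

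**The plan speaks of toxicity rates, not of a DLT rate.** DLTs under Section 5.2 are cycle 1 events, at least possibly drug-related, with several exclusions. Later or non-DLT toxicities, and efficacy, are not truncated by the 3+3 rule except through correlation with DLT. This stands and limits the point.

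**The detection table.** A reader might infer that its 0.77 at 10% incidence should become 0.57. That is 1 − 0.9^8 and describes only the 8 new patients. For the pooled 14 the figure is 0.77 for events unrelated to selection and 1 − (0.9/1.5) × 0.9^8 = 0.74 for DLT-type events. The table can stay.

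**Pooling is optional and contradicted.** With 14 additional patients the problem disappears. True, but the stated maximum of 32 assumes overlap, and the plan does not choose.

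**The estimates are preliminary and drive no decision rule.** That is fair. It limits the consequence to what is reported and does not make the interval right for DLTs.

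**Conclusion.** The point holds in a limited form. If the six escalation patients are pooled, the cycle 1 DLT rate at the MTD is biased low at every true rate above 0: by 0.043 at 0.20, 0.077 at 0.30 and 0.088 at 0.33. The planned upper limit is too low on average. Its miss rate varies with the true rate, from 0% below 0.193 to a maximum of 11.7% (at 0.297) for rates up to 0.333. The bias concerns cycle 1 DLTs and the events that constitute them. It is not a general fault in the toxicity or efficacy rates, and the MTD decision itself is unaffected.

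This rests on six patients at the MTD, as the definition requires, on 8 new patients, on independent outcomes at a common rate, and on a Clopper-Pearson interval. If all 14 are new, there is no bias. The statements on overlap in Sections 13.1, 13.2 and 3.3 cannot all be followed as they stand and must be reconciled.

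**What to change.** In Section 13.1:

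1. State whether the 14 include the six escalation patients, and bring the maximum in Section 13.2 and the accrual table in Section 3.3 into line (32 with overlap, 38 without).
2. If they are included, report the cycle 1 DLT rate separately for newly enrolled patients, with its own exact 90% interval.
3. For any pooled DLT rate, take the interval from the conditional distribution: six patients truncated at 1 DLT plus 8 binomial.
4. Leave other toxicity rates and efficacy rates pooled with the planned interval, and leave the detection table at 14 patients.

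The cost is SAP wording and a few lines of code. The price is precision: with 8 new patients the DLT interval can be 0.61 wide, against the stated 0.48. If the sponsor settles on 14 new patients instead, the planned interval and its width hold, with up to six more patients enrolled.

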1. OBJECTIVES

1.1 Phase I Objectives

1.1.1 Primary Objective

1.1.1.1 To determine the maximum tolerated dose (MTD), toxicity, and safety profile of AT13387 given weekly in combination with dabrafenib and trametinib in patients with BRAF-mutant metastatic or unresectable solid tumors.

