1.1.2 Secondary Objectives

1.1.2.1 To obtain preliminary estimates of the objective response rate (ORR) and progression-free survival (PFS) and document the 6-month PFS and 1-year overall survival (OS) of patients with BRAF-mutant metastatic or unresectable melanoma treated with AT13387 given weekly in combination with dabrafenib and trametinib.

1.1.2.2 To describe the pharmacokinetics of treatment with dabrafenib, trametinib, and AT13387.

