11. MEASUREMENT OF EFFECT

Although response is not the primary endpoint of the phase I portion of this trial, patients with measurable disease will be assessed by standard criteria. For the purposes of this study, patients should be re-evaluated every 8 weeks. In addition to a baseline scan, confirmatory scans will also be obtained at least 4 weeks following initial documentation of an objective response. Every attempt should be made to use a consistent imaging modality for each individual participant.

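### The only efficacy set named in section 13.1, the 14 patients at the MTD, is narrower than objective 1.1.2.1 on dose and wider on tumor type

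*Combined protocol and SAP*

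**What the plan says.** - **Objective (1.1.2.1).** ORR, PFS, 6-month PFS and 1-year OS are wanted in "patients with BRAF-mutant metastatic or unresectable melanoma treated with AT13387 given weekly in combination with dabrafenib and trametinib". No dose level is specified.
- **Enrolment (1.1.1.1).** The trial is run "in patients with BRAF-mutant metastatic or unresectable solid tumors", a wider population than melanoma.
- **Analysis set (13.1).** "Secondary endpoints that will be assessed for the 14 patients treated at the MTD are: objective response rate", then PFS, 6-month PFS and 1-year OS. The same section describes the cohort: "a total of 14 patients will be enrolled in an expansion cohort of patients with BRAF-mutant advanced solid tumors". MTD patients from the escalation phase may be counted in it.
- **Methods (13.1 and 13.3).** Rates get 90% exact binomial intervals; PFS and OS get Kaplan-Meier estimates with 90% intervals. Section 13.3 repeats the response and survival methods without naming a population.
- **Maximum size (13.2).** The 32 patients are made up of "four complete dose escalation cohorts of 6 patients each and the expansion cohort of 14 total patients at the MTD".
- **Data collection.** Section 3.1.2 requires measurable disease of everyone. Section 11 says "patients with measurable disease will be assessed by standard criteria", with re-evaluation every 8 weeks. Note o of the section 10 calendar collects survival every 6 months for up to 2 years. None of these depends on dose level.

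**The concern.** A statistician following section 13 would produce one set of efficacy estimates, from the 14 patients at the MTD. That set leaves out melanoma patients treated at other levels, whom the objective includes. It admits patients with other tumors, whom the objective does not.

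The tumor-type mismatch may matter more. The background sections report a 12% response rate to dabrafenib plus trametinib in BRAF-mutant colon cancer (2.1) and 76% in melanoma at the 150/2 doses (2.2.2.3). A response rate in 14 patients of mixed tumor type could therefore reflect case mix as much as the regimen.

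On dose, the trial collects response and survival on every patient but plans no estimate for those outside the 14 and no display by dose level. If level -1 also proved too toxic, the study would stop with no MTD. The set in 13.1 would then not exist, and 1.1.2.1 would have no analysis population.

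**Working it through.** **1. The two populations compared**

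| | Objective 1.1.2.1 | Section 13.1 |
|---|---|---|
| Dose | no restriction | MTD |
| Tumor type | melanoma | any BRAF-mutant solid tumor |

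Section 13.3 does not settle the difference, because it names no set. Its exploratory subsets concern prior therapy and on-study features such as dose reductions, not assigned dose level.

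**2. Counts**

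The plan's maximum reproduces if the six escalation patients at the MTD are counted within the 14: 4 × 6 + 14 − 6 = 32. Outside the 14: 32 − 14 = 18, or 56%.

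The 3+3 rule moves on after 0 of 3 DLTs, so cohorts need not fill. With three patients at each of levels 1 to 3 and the MTD at level 4, 3 + 3 + 3 = 9 fall outside and the total is 14 + 9 = 23.

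Section 13.1 also describes the 14 as additional. On that reading the maximum is 4 × 6 + 14 = 38, which equals the accrual table in 3.3, and 38 − 14 = 24 fall outside.

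**3. Interval widths, all tumor types**

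For x responders of n, the exact 90% limits are the 0.05 quantile of Beta(x, n − x + 1) and the 0.95 quantile of Beta(x + 1, n − x). At n=14 the widest interval is at x=7: 0.264 to 0.736, width 0.473. This agrees with the plan's upper limit of 0.48.

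| Set | n | Widest interval | Width | Narrower than n=14 by |
|---|---|---|---|---|
| MTD set in 13.1 | 14 | 0.264 to 0.736 | 0.473 | – |
| Levels 2–4, MTD at level 4, threes at levels 2 and 3 (3 + 3 + 14) | 20 | 0.302 to 0.698 | 0.396 | 16% |
| All treated, threes at levels 1–3 | 23 | 0.335 to 0.704 | 0.369 | 22% |
| Levels 2–4, MTD at level 4, full cohorts (6 + 6 + 14) | 26 | 0.327 to 0.673 | 0.347 | 27% |
| All treated, full cohorts | 32 | 0.344 to 0.656 | 0.312 | 34% |

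**4. Melanoma only**

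The documents give no melanoma share. Assume 50% to 100%, equal at every dose level, with 32 enrolled:

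- MTD set: n = 7 to 14, maximum width 0.646 to 0.473.
- All dose levels: n = 16 to 32, maximum width 0.443 to 0.312.

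At 50% the reduction is 1 − 0.443/0.646 = 31%. The MTD-only melanoma interval would then exceed 0.48.

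**5. Single dose levels**

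At most six escalation patients are planned per level. At n=6 the widest interval (x=3) is 0.153 to 0.847, width 0.694.

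**The case against.** Estimating efficacy at the MTD is a normal phase I choice, and 13.1 gives preliminary toxicity and efficacy estimates as the purpose of the 14-patient cohort. The endpoints are secondary and descriptive, with no hypothesis test. That stands, and it is why the MTD analysis should remain.

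Three stronger readings are tempting, and the documents do not support them:

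- **That efficacy data outside the MTD are discarded.** A reader might infer this from 13.1. But 13.3 restates the response and survival methods, and plans exploratory efficacy subsets, with no MTD limit. What is missing is a planned estimate and a defined set.
- **That 1.1.2.1 covers everyone given the combination.** It is limited to melanoma, so pooling all treated patients would not by itself match it.
- **That response by level would show whether more AT13387 adds activity.** Levels 2 to 4 share the same dabrafenib and trametinib doses and differ only in AT13387. But the levels are small and unrandomised. They mix tumor types and BRAF-inhibitor-naive with pretreated patients (3.1.1). Section 5.1 also allows intrapatient escalation, so starting level need not be the dose received.

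A narrower pooled interval is also not a pure gain, because it estimates a dose-mixed quantity. This limits the added set to a supportive role but does not remove the mismatch with the objective.

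**Conclusion.** The mismatch is real on both dose and tumor type, and section 13.3 does not resolve it. Between 9 and 18 patients have no planned efficacy estimate when the MTD is level 4 and the escalation patients at the MTD count within the 14; 18 needs every cohort to fill.

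Under those conditions the response interval for all tumor types narrows by about 22% to 34% at its widest. A reader might take a third as the expected gain, but that is the upper end. The size of the melanoma gain rests on an assumed share.

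The primary MTD objective is unaffected. The point is worth correcting because, as written, no planned analysis estimates the quantity in 1.1.2.1.

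**What to change.** Keep the 14-patient MTD analysis and add one paragraph to 13.1 defining a supportive efficacy set of all patients who received the combination. Report ORR, PFS, 6-month PFS and 1-year OS with the same 90% exact and Kaplan-Meier methods:

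- for melanoma patients (the set that matches 1.1.2.1) and for all tumor types;
- by assigned starting dose level and pooled;
- with a descriptive row pooling levels 2 to 4.

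Use the same definitions in 1.1.2.1, 13.1 and 13.3. Also reconcile whether the 14 are additional or a total, and 32 with the 38 in section 3.3.

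The cost is that paragraph plus one table and figure, with no new patients, visits or data. The downside is that pooled figures mix dose levels, tumor types and prior BRAF-inhibitor exposure, and intrapatient escalation blurs the by-level rows. All added rows should be labelled descriptive.
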